### **4.2 Secondary Objectives**

To determine if daily oral FTC/TDF is associated with comparable rates of adverse events (AEs) in transgender women and in transgender men compared to historical controls in non-transgender MSM.

## **5 STUDY DESIGN**

### **5.1 Study Overview**

This is a single center pharmacokinetic study of daily oral Truvada at the following FDA approved dose of one tablet containing 200 mg of emtricitabine (FTC) and 300 mg of tenofovir disoproxil fumarate (TDF) for PrEP using daily directly observed therapy (DOT).

The study will include 48 participants will be divided into two groups: one group will include 24 participants who currently describe their gender identity as “woman” or “transgender women”, or other transfeminine spectrum identity, and the second group will enroll 24 participants who identify as “man” or “transgender man”, or other transmasculine spectrum identity.

Each participant will be taking a single daily dose of study drug in DOT performed either via video calling, or at study visit, for a total study duration of 28 to 30 days (4 weeks).

Laboratory evaluations for HT (including testosterone, or estradiol) drug levels will be performed at enrolment, and after 4 weeks on study drug. Study drug levels will be monitored weekly in DBS while participants are on study.

Screening data will be reviewed to determine participant eligibility. Participants who meet all inclusion criteria and none of the exclusion criteria will be entered into the study.

The treatment regimen that will be used:

- Truvada at the following FDA approved dose of one tablet containing 200 mg of emtricitabine and 300 mg of tenofovir disoproxil fumarate

Total duration of participant participation will be up to 4 weeks, plus the 28 days of screening window period between screening visit and on study daily observed therapy. Total duration of the study is expected to be 9 -10 months.

## 5.2 Pharmacogenetic testing

Pharmacogenetics (PGx) studies the variability in drug response due to hereditary factors in populations. There is increasing evidence that individual's genetic background may impact the pharmacokinetics (absorption, distribution, metabolism and elimination) of drugs. The goal of the PGx analyses is to investigate a relationship between genetic factors and PK measures in I-BrEATHe, for example if there is potential unexpected or unexplained variation in drug levels. Blood samples collected for drug levels on DBS may be used for DNA extraction and PGx assessments. Participants will be specifically asked if they wish to participate in the genetic testing in the informed consent form.

## 6 CRITERIA FOR EVALUATION

### 6.1 Primary Endpoint

The primary endpoints for this study are the pharmacokinetics measures. These PK analyses are dependent on adherence and will be assessed at the end of study completion.

### 6.2 Secondary Endpoints

N/A

### 6.3 Safety Evaluations

AEs: Grade 1 and above as reported side effects on a structured instrument

## 7 PARTICIPANT SELECTION

### 7.1 Study Population

I-BrEATHe is a sub study of the TRIUMPH study with an anticipated overall cohort of 188 transgender participants. Volunteers who are participants in the larger TRIUMPH project may be recruited to participate in this sub study, however the I-BrEATHe sub study may also enroll volunteers outside of the TRIUMH study.

Up to 48 volunteers who meet the inclusion and exclusion criteria will be eligible for participation.

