#### **9.4.4 Participant Replacement Instructions**

Participants who withdraw from the study prior to completion or who fail to adhere to the DOT regimen may be replaced.

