#### **9.6 Measures of Treatment Adherence**

Daily adherence will be directly observed by participants taking part in real time DOT video calls, or witnessed by study staff at the study visit if the drug is taken at the clinic. Study staff will monitor the FTC/TDF tablet be placed into the mouth, swallowed, and the mouth opened to verify the table is no longer present. Alternate documentations of pill taking as described in 9.4.1 may be used as back up measures if access to video capacity is impossible for participant. DOT will be recorded daily by the study team to document on the Drug Dispensation, Hormones and DOT log. Repeated failure to adhere to the DOT regimen will lead to discontinuation from study participation.

If participant fails to connect with study staff for the call, study staff will make every possible attempt to connect with participant. If participant misses the call and does not provide back up evidence of pill taking, it will be considered a missed dose.

If participant misses two or more study drug doses, the participant will be excluded from study participation.

DOT calls will capture hormone therapy adherence as well, which may be either directly observed if feasible, or verbal self-report. Hormone adherence will be captured on the Drug Dispensation, Hormones and DOT log.

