### **15.4 Sample Size**

A sample size of 48 (24 trans women and 24 trans men) allows detection of a difference of 0.52 log difference (1.68 fold difference) in TFV-DP from dried blood spots with 81% power on a two-sided 0.05 level test at any time point between our trans participants and MSM historical controls. A difference of 0.70 log (2.0 fold difference) can be detected between either group (trans men or women) and MSM historical controls with 80% power on a two-sided 0.05 level test. This is sufficient to determine if the differences in drug

concentrations observed in iPrEx OLE between MSM and trans women were due to interactions with feminizing hormone drug-drug interactions.

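### The 81% and 80% power need 24 + 24 analysed participants, but the enrolment, replacement and PK-set rules do not ensure that number; one missed dose costs a participant without a clear route to replacement.

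*Combined protocol and SAP*

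**What the plan says.** **Number behind the power.** Section 15.4: "A sample size of 48 (24 trans women and 24 trans men) allows detection" of a 0.52 log difference "with 81% power on a two-sided 0.05 level test at any time point between our trans participants and MSM historical controls". For one group, at 80% power and the same significance level, it says: "A difference of 0.70 log (2.0 fold difference) can be detected between either group (trans men or women) and MSM historical controls". The synopsis repeats both statements. Neither place gives a dropout rate, an SD or the number of historical controls.

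**Number enrolled.** Section 7.1: "Up to 48 volunteers who meet the inclusion and exclusion criteria will be eligible for participation". Section 5.1 gives 48 as the study size and 7.5.2 gives it as the recruitment aim, with up to 80 people screened to reach the enrolment target.

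**Removal.** Section 9.6: "If participant misses two or more study drug doses, the participant will be excluded from study participation". A dose with no documentation counts as missed (9.4.3, 9.6). Section 14 lists two or more undocumented failed calls as a protocol violation and leaves it to the sponsor whether a violation leads to withdrawal.

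**Analysis set.** Section 15.1 restricts the pharmacokinetic analysis to eligible, enrolled participants who received all doses.

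**Replacement.** Section 9.4.4 says that participants who withdraw early or "fail to adhere to the DOT regimen may be replaced". Section 12.4 (Replacement of Participants) likewise only permits replacement of those who withdraw from treatment. Neither says whether replacements are additional to the 48, whether they come from the same gender group, or when replacement stops.

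**The concern.** The enrolment figure equals the analysis figure, so the stated power has no margin. Any participant who leaves the PK set and is not replaced takes the power below 81% or 80%.

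The rules also use two different missed-dose criteria. Compare three participants:

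| Doses missed | 9.6 and 14 | Replaceable under 9.4.4 or 12.4? | In the PK set (15.1)? |
|---|---|---|---|
| 0 | stays | not needed | yes |
| 1 | stays; below the threshold | not clearly: has neither withdrawn nor reached the stated DOT-failure threshold | no |
| 2 or more | excluded (9.6), or sponsor decides (14) | yes, optional | no |

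The middle row is the gap. That participant completes the study, occupies one of the 48 places and contributes nothing to the primary comparison at any time point. Even full use of the replacement clauses need not restore 24 + 24. Because replacement is not tied to gender group, losses may also fall unevenly on a per-group comparison that is planned to detect only a 2-fold difference.

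**Working it through.** **1. Inputs.** From 15.4: n = 48 pooled at 0.52 log with 81% power; n = 24 per group at 0.70 log with 80% power; two-sided 0.05. The logs are natural, since exp(0.52) = 1.68 and exp(0.70) = 2.01. From 9.4.1: 28 daily doses. Not stated: the SD of log TFV-DP (s), the number of MSM controls (m), and any loss or miss rate.

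**2. The plan's own figures.** They cannot be reproduced independently without s and m, but two power statements allow both to be solved. By normal approximation, SE = difference / (z for 0.975 + z for power), and SE² = s²(1/n + 1/m).

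- Pooled: SE = 0.52 / 2.838 = 0.1832; SE² = 0.03358.
- Per group: SE = 0.70 / 2.802 = 0.2499; SE² = 0.06243.
- Subtracting: s²(1/24 − 1/48) = 0.02885, so s² = 1.385 and s = 1.18.
- Then 1/m = 0.03358/1.385 − 1/48 = 0.00341, so m is about 293.

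Using ln 2 = 0.693 for the 2-fold difference gives s = 1.15 and m about 223. Allowing for rounding of the powers, m runs from about 167 to 473 and s from 1.13 to 1.20. The two statements are thus consistent with each other when exactly 48 and 24 are analysed, with no loss.

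**3. Who enters the PK set.** Assume independent misses with probability p per dose (an assumption, not a figure in the protocol). P(none) = (1 − p)^28; P(exactly one) = 28p(1 − p)^27.

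| p | None | Exactly one | Two or more | Expected PK set of 48 |
|---|---|---|---|---|
| 0.5% | 86.9% | 12.2% | 0.9% | 41.7 |
| 1% | 75.5% | 21.3% | 3.2% | 36.2 |

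At these rates almost all the loss comes from a single missed dose, not from the two-dose rule.

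**4. Power at the reduced number**, with s and m held fixed: power = Φ(difference/SE − 1.960). Worked for s = 1.177, m = 293:

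- 42 pooled: SE = 0.1942; 0.52/0.1942 − 1.960 = 0.718; power 76.4%.
- 36 pooled: SE = 0.2078; 2.502 − 1.960 = 0.542; power 70.6%.
- 21 per group: SE = 0.2658; 2.633 − 1.960 = 0.673; power 75.0%.
- 18 per group: SE = 0.2858; 2.449 − 1.960 = 0.490; power 68.8%.

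The other solution (s = 1.15, m = 223) gives 76.6%, 71.0%, 75.1% and 69.0%.

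**5. Sensitivity.** For m anywhere from 48 to 1000, with s refitted to each stated power, the same four results are 76-78%, 70-75%, 75-76% and 68-72%. The conclusion does not hinge on the solved values.

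**6. Other analysed numbers** (the two solutions of step 2). 43 analysed as 22 + 21: about 77% pooled; 77% for the group of 22 and 75% for the group of 21. 38 analysed as 19 + 19: about 73% and 71%.

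**The case against.** The strongest reply is that the protocol already has the remedy. Replacement is permitted in two places, one of them naming DOT non-adherence, and up to 80 people may be screened. At a single site whose investigators are the sponsors, those who decide on replacement are those who need the power. Missed doses are also made less likely: audio calls, self-filmed video and text messages count as documentation (9.4.3, 10.4), entrants must be judged likely to adhere (7.4), and visit incentives encourage the calls (7.5.3).

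Much of this stands, and it rules out three stronger readings.

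- *A reader might infer that enrolment is capped at 48, so 24 + 24 cannot be reached.* Section 7.5.2 calls 48 an aim, and a hard cap in 7.1 would leave the replacement clauses unable to operate once 48 were enrolled. The documents are unclear on this; they do not forbid replacement.
- *A reader might infer that the two-dose exclusion is the main drain.* It is not at the miss rates considered here, and section 14 leaves withdrawal after a violation to the sponsor, which must itself be reconciled with 9.6.
- *A reader might infer a known power loss.* No loss or miss rate is stated; every rate here is assumed.

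The reply does not meet the one-missed-dose case, to which neither replacement clause clearly applies. Permission to replace is also not a commitment to reach 24 analysable per group: 7.5.2 ties the 80 screenings to the enrolment target, not to the analysis set.

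**Conclusion.** The point holds in this form: the stated power requires every one of 48 participants to be in the PK analysis, and the rules allow that outcome without ensuring it. The chief cause is the mismatch between the two-dose criterion in 9.6 and 14 and the all-doses criterion in 15.1.

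The size is moderate. Without replacement, the pooled comparison loses about 4-5 points of power at a 0.5% miss rate and about 10 at 1%; the per-group comparison loses about 5 and 11. This rests on independent misses at an assumed rate, no other withdrawals, a normal approximation, and an SD and control number solved from the plan's own powers. Clustered misses or further withdrawals would change the figures, but not the finding that 15.4 leaves no margin.

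**What to change.** 1. Reconcile 15.1 with 9.6 and 14, so that the PK set and the removal and replacement trigger use the same missed-dose criterion. Which criterion is for the sponsor to decide.
2. In 7.1, 9.4.4 and 12.4, state whether 48 means enrolled or PK-analysable and whether replacements are additional to 48. Make replacement within the same gender group, up to the 80 screenings already allowed.
3. Alternatively, if enrolment stops at 48, restate the power in 15.4 and the synopsis at the expected analysable number, with the assumed loss rate shown. For example, 43 analysed as 22 + 21 gives about 77% for 0.52 log and 75-77% for 0.70 log.
4. In either case, report the SD and the number of MSM controls used.

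**Cost.** Wording in a few sections, plus either a slightly lower stated power or some extra participants. How many depends on the criterion chosen, by enrolment per group = 24 / (proportion analysable). If only participants with two or more missed doses are lost, 24/0.991 = 24.2 and 24/0.968 = 24.8, so 25 per group at either assumed miss rate. If every dose is required, 24/0.869 = 27.6 and 24/0.755 = 31.8, so 28 or 32 per group (56 or 64 in total). The last would need 64 of the 80 screened, or 80%, to enrol. The extra cost is therefore small only if the criteria are aligned in a way that keeps one-miss participants in the analysis, or if misses are rare.

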### 7.2 Inclusion Criteria:

All subjects:

- HIV antibody seronegative (negative HIV rapid test),
- 18 years or older,
- Has a smart phone with access to two-way video call capability,
- Willingness to be contacted for a short call every day for 4 weeks,
- Adequate renal function (creatinine clearance  $\geq 60$  ml/min estimated by the Cockcroft Creatinine Clearance Formula),

- Provides written informed consent,

For Transgender women:

- Male assigned sex at birth, and self-reported current gender identity as “woman” or “transgender women”, or other trans-feminine spectrum identity,
- Current feminizing Hormone Therapy (HT) use for at least 6 months,

For Transgender men:

- Female assigned sex at birth, and self-reported current gender identity as “man” or “transgender man”, or other trans-masculine spectrum identity,
- Current masculinizing Hormone Therapy (HT) use for at least 6 months with testosterone

### 7.3 Exclusion Criteria

- Expects to change or discontinue current HT use during the 4 weeks study period,
- Signs of symptoms of acute viral syndrome,
- Use of FTC or TDF in the past 90 days
- Receiving ongoing therapy with any of the following:

*ART, including nucleoside analogs, non-nucleoside reverse transcriptase inhibitors, protease inhibitors or investigational antiretroviral agents interferon (alpha, beta, or gamma) or interleukin (e.g., IL-2) therapy, aminoglycoside antibiotics, amphotericin B, cidofovir, systemic chemotherapeutic agents, other agents with significant nephrotoxic potential, other agents that may inhibit or compete for elimination via active renal tubular secretion (e.g., probenecid), and/or other investigational agents*

- Renal insufficiency documented as Creatinine Clearance < 60 ml/min
- For masculine-spectrum identifying persons, positive pregnancy test at screening
- At enrollment, has any other condition or factor that, based on the opinion of the investigator or designee, would preclude provision of informed consent; make participation in the study unsafe; complicate interpretation of study outcome data; or otherwise interfere with achieving the study objectives.

### 7.4 Eligibility determination

Eligibility criteria must be carefully assessed at the screening visit and confirmed at the enrolment visit prior to drug dispensation. Eligibility for recruitment will be determined by the study team based on the data collected at the screening visit. Eligibility assessment will happen between the screen and enrolment visits, and will include reviewing medical record with medical exam, medical history and ongoing medications, reviewing testing results for HIV and chemistries. All clinical and laboratory assessments of eligibility must be performed and reviewed within 28 days of initiating the screening process and all screen results available prior to enrolment. If all inclusion criteria are met, and participant

is deemed likely to adhere to the daily observed therapy regimen, participants will be confirmed for their pre-scheduled enrolment visit.

At the enrolment visit, an HIV rapid test will be repeated. If the rapid HIV test results are negative, and no other exclusion criteria are identified, participant will be enrolled into the study, and study medication will be dispensed.

## **7.5 Recruitment and retention**

### **7.5.1 Study site**

The study site will have the capacity to comply with the protocol, study-specific procedures, and all applicable regulations. The site will have a reception area or a waiting area, a physical examination room, and/or counseling room, a study storage area or pharmacy, a data management area with locked cabinets or equivalent, computer access, laboratory facilities, and/or a phlebotomy area.

### **7.5.2 Recruitment**

The current recruitment aim for this study is 48 participants, as described in sections 5.1 and 7.1. To reach the target enrolment number, up to 80 potential participants may be screened.

The recruitment strategies may include one or several of the following:

- Sending a “Dear Doctor” letter to healthcare providers who have a large number of transgender patients and asking for provider referral,
- Advertising the I-BrEATHe study on social media platforms,
- Using principal investigators’ database of participants who were enrolled in studies previously conducted at the UCSF CoE-T. Volunteers in this CoE-T database have given consent to be contacted for future research,
- Asking participants who have enrolled in the main TRIUMPH study,
- Inviting UCSF CoE-T staff who may be good candidates,
- Using word of mouth,
- Posting flyers in targeted areas, agencies, clinics, Community Based Organizations, or Triumph community mobilization activities

These approaches, along with input from our community advisory boards and our current programs that serve transgender communities, will be used in recruitment efforts.

Volunteers interested in I-BrEATHe will be able to contact a special phone number created especially for the study. Callers to this number will be routed to the study team. If a study staff member is unable to answer the phone, there will be an outgoing message which will allow leaving a voicemail for a call back, as well as information on clinic drop-in hours for those with unreliable phone service. Study team members may also be available at community mobilization activities to recruit. Efforts will be made to pre-screen inquiries by phone, at events, or at the referring clinics for eligibility based on inclusion criteria. Participants will then be referred to the study site for screening.

### 7.5.3 Retention

Given to the lack of evidence to guide trans-specific recruitment and retention strategies or trans-inclusive implementation practices, we will use the expertise of the CoE-T to engage with our transgender identified participants. The lack of attention to the sociocultural context of trans women's lives especially and adaptations from other populations (i.e. MSM) have proven insufficient and unacceptable by the trans communities, evidenced by low recruitment and retention in clinical trials. Our study team has an understanding of the pervasive role of trauma in transgender people's lives, specifically trauma that is often enacted in medical settings and can lead to the avoidance of medical care, including HIV testing and prevention. For transgender people, feeling safe and being able to trust one's provider is a pre-requisite to successful engagement and retention in healthcare. Trust must be established within and throughout the community, as transgender social networks are tightly knit.

Therefore, the I-BrEATHe study staff will be selected based on heightened sensitivity to transgender issues, appropriate training in transgender competency, and will possibly be members of the transgender communities themselves. Staff will be in close contact with the participants. Staff will remind participants by e-mail and/or telephone of their upcoming appointments. The participants will be interacting daily via video calls which can help create a relationship of trust. Participants will receive monetary incentive at their visit to the study site to encourage the video calls participations during the previous week. These incentives will be reviewed by the UCSF IRB to ensure that they are not excessive and coercive. At the end of the study, the participants may be invited to an appreciation event.

## 8 CONCURRENT MEDICATIONS

All participants should be maintained on the same medications throughout the entire study period, as medically feasible, with no introduction of new chronic therapies.

### 8.1 Allowed Medications and Treatments

Standard therapy is allowed except for treatments noted in the exclusion criteria described above and as noted in the prohibited medications section below.

### 8.2 Prohibited Medications and Treatments

The following medications are prohibited during the study and administration will be considered a protocol violation:

ART, including nucleoside analogs, non-nucleoside reverse transcriptase inhibitors, protease inhibitors or investigational antiretroviral agents, interferon (alpha, beta, or gamma) or interleukin (e.g., IL-2) therapy, aminoglycoside antibiotics, amphotericin B, cidofovir, systemic chemotherapeutic agents, other agents with significant nephrotoxic potential, other agents that may inhibit or compete for elimination via active renal tubular secretion (e.g., probenecid), and/or other investigational agents

## 9 STUDY TREATMENT

### 9.1 Method of Assigning Participants to Treatment Groups

Participants will be separated into two groups based on their gender identity, and all participants will undergo the same study procedures, to the exception of a pregnancy test for female assigned at birth transmasculine people, when appropriate (see study procedures below).

### 9.2 FTC/TDF

#### 9.2.1 FTC/TDF Formulation

FTC/TDF is a fixed-dose co-formulation of FTC and TDF disoproxil fumarate (TDF). Each FTC/TDF tablet contains of 200 mg of FTC and 300 mg of TDF (equivalent to 245 mg of tenofovir disoproxil). Please refer to the full prescribing information for FTC/TDF for more information regarding drug information, side effects, and storage conditions. The Truvada pill is a blue oblong pill to be swallowed with some liquid.

